2.2. Study design, participants, and randomization

We are conducting a randomized, double-blind, placebo-controlled study to investigate the effects of intranasal oxytocin (24 IU, 4 times/day, for 8 weeks) in adults with obesity (BMI ≥ 30 kg/m²), aged 18–45 years. We randomized 61 individuals to achieve our target evaluable population of at least 50 participants who complete the 8-week treatment period. Participants were stratified by

biological sex (female/male) and obesity class (class 1: BMI 30.0–34.9 kg/m², class 2: BMI 35.0–39.9 kg/m², class 3: BMI ≥40.0 kg/m²) and randomized 1:1 to receive oxytocin or placebo. The unblinded study pharmacist performed randomization. All other study staff and participants are blinded to treatment assignment. We recruited participants through Massachusetts General Hospital (MGH) and advertisements online/in the surrounding community. Table 1 summarizes the inclusion and exclusion criteria of the study.

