2.4. Study procedures and assessments

Study time points comprise the screening visit to determine eligibility, two baseline visits (the second one includes randomization and treatment initiation after baseline assessments are completed), on-treatment study time points (week 2, 4, 6, and 8 visits), and a final week 14 follow-up visit to assess sustained treatment effects and safety.

Study visits take place at the MGH Translational and Clinical Research Center and the Athinoula A. Martinos Center for Biomedical Imaging. We obtain and manage study data using a web-based secure Research Electronic Data Capture (REDCap) system [38].

See Figure 2 for an overview of the study design, including visits, endpoints, and assessment methods. Table 2 provides a detailed list of study procedures/assessments at each study visit.

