2.5.3. Statistical analysis plan

Figure 3 shows our statistical analysis plan. We will perform statistical analyses using R statistical software, and appropriate R packages [54]. For continuous endpoints (see 2.3.), we will apply mixed model regression for repeated measurements (MMRM). We will consider the between-group (oxytocin versus placebo) difference in the least-squares mean change of each individual endpoint variable from baseline to each follow-up study time point of interest as the response in MMRM; the change from baseline to week 8 study time point (end of treatment) will be of primary interest (see 2.3.). Treatment group (oxytocin versus placebo), study time point (visit), and treatment group*study time point interaction will be included as fixed factors in MMRM. The baseline value of the endpoint variable and stratification factors (biological sex, BMI) will be entered as covariates. Additional covariates may be considered as appropriate. The intercept and time slope of individual participants will constitute random effects. Parameters of MMRM will be estimated via restricted maximum likelihood (REML). Depending on the distributional characteristics of the data, we may apply logarithmic transformations and/or robust statistical methods. We will adjust for multiple comparisons where appropriate via the approach of Hothorn, Bretz, and Westfall based on single-step simultaneous inference using a joint multivariate t-distribution [55]. We will use a modified intention-to-treat approach for efficacy analyses, including all randomized participants with available data for at least the second baseline visit

(randomization/initiation of treatment) and the first on-treatment study time point. We will apply a per-protocol approach for sensitivity analysis, including only randomized participants who complete the study and demonstrate $\geq 80\%$ adherence to treatment. We will carefully examine patterns of any missing data regarding their relationships with the outcomes of interest and incorporate uncertainty due to missing data with multiple imputations where applicable.

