
Abbreviations: BMI, body mass index; EKG, electrocardiogram; ALT, alanine transaminase; AST, aspartate transaminase; MRI, magnetic resonance imaging; DXA, dual-energy X-ray absorptiometry.

Table 2. Study procedures at individual study time points.

Assessments	Screen	BL		ON-T (oxytocin versus placebo)				OFF-T
		BL1	BL2	W2	W4	W6	W8	W14
Screening and safety								
• Medical history and physical exam, MMSE	X	X	X	X	X	X	X	X
• Screening/safety labs (CBC, TSH, urine drug screen (at screen only); CMP, HbA1c)	X		X	X	X		X	X
• EKG	X			X			X	
• M.I.N.I.	X							
• Adverse events monitoring, review of concomitant medication, pregnancy test (urine/serum hCG) in females	X	X	X	X	X	X	X	X
Anthropometric measurements (height, weight, %IBW ^a , BMI ^b , WHR ^c)								
	X	X	X	X	X	X	X	X
Energy expenditure, body composition, and fat metabolism								
• Indirect calorimetry (REE)		X				X	X	
• DXA (total fat mass, lean body mass)		X					X	
• MRI (abdominal and thigh measures)		X					X	
• 1H-MRS (liver fat)		X					X	
• Fat biopsy		X		X				
Caloric intake								
• Breakfast test meal (experimental assessment of caloric intake)		X				X		
• 4-day food record (typical eating)		X	X		X	X	X	X
• 24-hr food recall (caloric intake immediately preceding visit)		X	X		X	X		
Laboratory assessments								
• Blood for metabolic profile (e.g., insulin sensitivity, lipid panel, hsCRP, appetite-regulating hormones), gonadal steroids, leukocyte RNA, DNA (optional)			X	X	X	X	X	X
• 24h urine (e.g., cortisol, creatinine)		X					X	
• Stool (e.g., microbiome; optional)			X		X		X	
• Hair (e.g., cortisol; optional)			X				X	
Neuroimaging								
• Food cue task (fasting and post-meal): VTA, OFC, anterior insula, hypothalamus			X		X			
• Impulse control tasks (Stop-Signal Task; Multi-Source Interference Task [optional]) (fasting): dPFC, dACC, preSMA			X		X			
• Handedness questionnaire		X						
Psychological, behavioral, and quality of life assessments								
• Physical activity (PPAQ ^d)	X				X	X		X
• Appetite (VAS ^e), eating behavior and attitudes (EDEQ ^f , DEBQ ^g , EADES ^h , TFEQ ⁱ)		X	X		X	X	X	X
• Reward-related food motivation (BIS/BAS ^j , CTT ^k , PFS ^l) and reward-related behaviors and choices			X		X			X

(Probabilistic Reward Task and Social Reward Task, TEPS ^m ; optional)					
• Impulse control and compulsivity (Delay Discounting Task, Reversal Learning Task, BIS-11 ⁿ , BOCS ^o , SRS ^p ; optional)		X		X	

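### As written, the efficacy set requires week-2 data, so a participant with none who is weighed at week 4, 6 or 8 drops out of the primary analysis (minor)

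*Combined protocol and SAP*

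**What the plan says.** Section 2.5.3 applies a modified intention-to-treat (mITT) approach to the efficacy analyses. The set contains "all randomized participants with available data for at least the second baseline visit", and the sentence continues "randomization/initiation of treatment) and the first on-treatment study time point". The two conditions are joined by 'and'.

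Section 2.4 lists the "on-treatment study time points (week 2, 4, 6, and 8 visits", so the first of them is week 2. In Table 2 the row "Anthropometric measurements (height, weight, %IBW" and so on is marked at every visit, including weeks 2, 4, 6 and 8.

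The primary endpoint is percent change in weight from baseline to week 8 (section 2.3 and Figure 3). It is analysed by a mixed model for repeated measurements, fitted by restricted maximum likelihood with a random intercept and slope.

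The one other efficacy set is a "per-protocol approach for sensitivity analysis, including only randomized participants who complete the study" with at least 80% adherence. Multiple imputation is to be used where applicable. Figure 3 names mITT and multiple imputation but does not define the set in any other way.

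**The concern.** Membership of the primary analysis set depends on what happened at one particular visit after randomisation. The mixed model does not need a value at that visit: a participant with weights at baseline and week 8 contributes directly to the week-8 contrast whether or not week 2 was recorded. The rule can therefore discard an observed value of the primary endpoint from a randomised participant. That departs from intention-to-treat for no analytical gain, and it costs some precision in a trial of 61 people.

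**Working it through.** **1. Which visit, and what counts as data.** Section 2.4 makes week 2 the first on-treatment time point. The condition covers all efficacy endpoints, yet Table 2 schedules no calorimetry, DXA, abdominal MRI, liver spectroscopy or test meal at week 2. A condition requiring each endpoint's own value at week 2 would empty those analyses. The workable reading is at participant level: the person must have some week-2 data. If one instead reads it as the first scheduled on-treatment assessment of each endpoint, the answer for weight is still week 2.

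**2. Who is affected.**

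| Participant | Current mITT set | At least one on-treatment weight |
|---|---|---|
| Attends week 2 with any data, then leaves | In | In, if weighed |
| Leaves before week 2, never weighed again | Out | Out |
| No week-2 data, weighed at week 4, 6 or 8 | **Out** | **In** |

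Only the third row involves discarded weights.

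**3. Does another planned analysis cover the third row?** The per-protocol set is drawn from randomised participants and has no week-2 condition. It is not nested in the mITT set, and it could include such a person if they completed and were adherent. It also removes non-completers and non-adherers, so a comparison of the two sets does not isolate the week-2 rule. No text says that multiple imputation brings back anyone outside the mITT set.

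**4. The plan's own figure.** Section 2.5.1 gives a two-sample t-test, two-sided 5%, a difference of 3.2 kg, an SD of about 4 kg and 25 per arm. The standardised difference is 3.2/4 = 0.8. The normal approximation gives 25 per arm and 80.7% power, which reproduces the plan. The exact t-test uses noncentrality 0.8/√(1/n₁ + 1/n₂). For 25 + 25 this is 0.8/√0.08 = 2.83 on 48 degrees of freedom, giving 79.1% power.

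**5. Assumed losses.** The documents give no count, so 0 to 3 per arm is an assumption. The same formula is used throughout. The 31 + 30 split is assumed from 1:1 allocation of 61, with no other missing data.

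| Lost per arm | Power from 31 + 30 | Detectable at 80% power | Power from 25 + 25 | Detectable at 80% power |
|---|---|---|---|---|
| 0 | 86.7% | 2.92 kg | 79.1% | 3.23 kg |
| 1 | 85.5% | 2.97 kg | 77.4% | 3.30 kg |
| 2 | 84.3% | 3.02 kg | 75.6% | 3.38 kg |
| 3 | 82.9% | 3.08 kg | 73.6% | 3.46 kg |

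From 61, power is 81.5% with 4 lost per arm and goes just below 80% (79.9%) only with 5.

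**6. Does the model lose anything by keeping these people?** The variance of the week-8 mean in an arm of 25 was computed by generalised least squares, with random intercept and slope and separate visit means. One to three participants lacked week 2 only, and nine assumed combinations of slope SD and residual SD were tried. If these participants are kept, the variance relative to complete data is 1.00 in every case. If they are dropped, it is 25/24 = 1.042, 25/23 = 1.087 or 25/22 = 1.136.

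**The case against.** - **The affected group is very narrow.** This stands. The text asks for available data, not an available weight, and week 2 also includes an examination, safety bloods, an EKG, adverse-event review and a fat biopsy. Only someone with no week-2 data at all who later returns is excluded. The documents report no such case.
- **The plan may have meant at least one on-treatment value.** Possibly, but it does not say so. If that was the intention, the same one-phrase edit settles it.
- **The 25-per-arm base overstates the loss.** This stands. The plan says "We randomized 61 individuals to achieve our target evaluable population of at least 50 participants who complete the 8-week treatment period", but the mITT set also admits non-completers who have week-2 data, and the model uses their weights. The 61-participant base is the fairer one, although it is a best case because it assumes no other missing data.
- **The replacement is also a condition met after randomisation.** True. It is only looser, and its gain is that weights already observed are no longer thrown away.
- **The plan already addresses missing data.** In part. It commits to examining missingness patterns and to multiple imputation where applicable. That lowers the severity, but it does not clearly restore excluded participants.

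Two stronger readings are tempting. A reader might infer that the per-protocol set is a subset of the mITT set, so that the week-8 weight of such a person is lost to every analysis. The definitions do not support this (step 3). A reader might also infer that the rule biases the treatment effect. The documents give neither the number affected nor its split by arm, so no bias can be asserted or sized.

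**Conclusion.** The point holds as a defect of wording in the primary analysis set. Taken literally, section 2.5.3 excludes a randomised participant with no week-2 data even when the week-8 weight was recorded, and the planned model gives no reason for doing so. The impact is unknown and may be nil. Under the assumed loss of 1 to 3 per arm, power falls by 1.2 to 3.8 percentage points from 61 randomised (86.7% to between 85.5% and 82.9%), and by 1.7 to 5.5 points on the pessimistic base of 25 per arm (79.1% to between 77.4% and 73.6%). These figures rest on the plan's kilogram basis of 3.2 kg and SD 4 kg, a simple t-test and the assumed counts. Severity: minor.

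**What to change.** For the primary endpoint, define the set as all randomised participants, analysed as randomised, with a baseline weight and at least one weight at the week 2, 4, 6 or 8 visit. Let every available weight enter the mixed model. Keep the current week-2 set as a sensitivity analysis, so that the effect of the rule can be seen.

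Optionally, add a sensitivity analysis of all 61 randomised participants with a stated assumption for those who have no on-treatment weight. Under missing-at-random these participants leave the estimate essentially unchanged, so this addition is informative only under a not-at-random assumption.

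The cost is one phrase in the analysis plan and minor programming, with no new data. Section 2.2 states that, apart from the pharmacist, "All other study staff and participants are blinded to treatment assignment". This describes the position when the plan was written and does not show that the blind is still in place. If it is, make and date the change before unblinding. The downside is that people who miss visits may also have taken less study drug, so the estimate could be somewhat smaller than in the current set. The documents give no figure for this.

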2.6. Study drug, study drug administration, and treatment adherence

The study drug, 24 IU of intranasal oxytocin (Syntocinon[®] Nasal Spray, Mylan, Switzerland) or placebo (containing the same inactive ingredients as Syntocinon[®]), is applied as 3 sprays per nostril, 4 times per day (20–30 minutes before main meals and at bedtime), for an 8-week treatment period. We used the same intranasal oxytocin dose (24 IU) in our prior studies of men showing significant effects on food reward, homeostatic, and cognitive control-related

neurocircuits, impulsivity, and caloric intake [21,29,30,56]. Further, this oxytocin regimen (versus placebo) significantly reduced weight in a small study of 20 adults with obesity [35]. In the latter pilot study, as well as in a review article of 38 randomized controlled trials (n = 926 participants) administering up to 40 IU of intranasal oxytocin (4 times/day) over up to 13 weeks [57], no serious adverse events were reported and there were no differences in adverse events between oxytocin and placebo groups.

To assess treatment adherence, we ask participants to complete and return a drug diary at each visit during the 8-week treatment (Table 2). Adherence is determined per the drug diary reflecting $\geq 80\%$ study drug administration. Drug accountability is assessed by study staff throughout the study, and subjects are asked to return all used and unused study drug at each visit.

2.7. Study monitoring, quality assurance, and protection of human subjects

Source documents are monitored and reviewed by study staff throughout the study, and medical and research records are maintained appropriately per regulatory and institutional requirements for the protection of confidentiality of participants. The study is conducted in full conformity with federal regulations and institutional requirements (Declaration of Helsinki; regulations for the protection of human patients of research; Good Clinical Practice), including periodic and expedited safety reporting. An independent data and safety monitoring board consisting of a biostatistician and two endocrinologists met before study initiation and regularly thereafter to monitor progress and safety. Our study is registered on ClinicalTrials.gov (NCT03043053).

3. Results

Table 3 presents characteristics of the randomized study sample, which has almost equal biological sex distribution and racial (38% non-White) and ethnic (20% Hispanic/Latino) diversity.

4. Discussion

We have carefully designed and powered this randomized controlled double-blind trial to determine the efficacy, safety, and underlying mechanisms of 8-week oxytocin administration versus placebo as a novel weight-loss therapeutic in a diverse population of adults with obesity. Our study builds on solid evidence from animal models [10–12] and a preliminary clinical trial [35]. The innovative approach uses metabolic, neuroimaging, and behavioral assessments to provide important information about oxytocin mechanisms and actions.

Disclosures

Acknowledgments

The authors would like to express their deepest gratitude to the entire study team including study physicians, psychologists, nurse practitioners, dietitians, fellows, clinical research coordinators, and student interns for managing and conducting the study. The authors would like to thank all study participants for their participation.

Funding

This work was supported by National Institutes of Health (NIH) Grants R01 DK109932 ([name]) and K24 MH120568 ([name]), core services from the Nutrition Obesity Research Center of Harvard P30 DK040561, a Boston Nutrition Obesity Research Center pilot grant P30 DK046200 ([name]), and a Massachusetts General Hospital Department of Medicine Eleanor and Miles Shore Fellowship Award ([name]).

Conflict of Interest Statement

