2.1. Study rationale, preliminary data, and aims

Given promising preclinical and preliminary clinical findings indicating beneficial effects of oxytocin on eating behavior, metabolism, and weight loss [12,35], investigation of the efficacy and safety of prolonged intranasal oxytocin administration as a potential weight-loss therapeutic in humans is warranted. Further, exploring mechanisms underlying the metabolic actions of oxytocin is of high interest. Our clinical trial addresses these key research questions by determining whether 8-week intranasal oxytocin promotes weight reduction in adults with obesity and investigating the neural and metabolic pathways leading to the proposed oxytocin effects on body weight.

We demonstrated that a single dose of 24 IU intranasal oxytocin administered to fasting men across the weight spectrum reduced caloric intake at a test meal, increased fat utilization, and improved insulin sensitivity [21]. In a crossover functional magnetic resonance imaging (fMRI) study of men with overweight or obesity, we found that 24 IU intranasal oxytocin (versus placebo) reduced brain activation to high-calorie food images in the VTA, the origin of the mesolimbic dopaminergic reward system, and other hedonic (e.g., orbitofrontal cortex [OFC] and anterior insula) and homeostatic (e.g., hypothalamus) areas [30], and reduced functional connectivity between the VTA and reward-related brain regions (e.g., amygdala and insula) [29]. In contrast, oxytocin increased activation in cognitive control-related brain regions (e.g., dorsal anterior cingulate cortex [dACC] and dorsolateral prefrontal cortex [dlPFC]) [30] and improved impulse control, as assessed using a behavioral task previously linked to eating behavior [36].

Thus, we hypothesize that 8-week intranasal oxytocin will reduce food intake (by decreasing reward-related and homeostatic drive to eat and increasing eating-related impulse control) and

body fat and weight (via effects on eating behavior, REE, and fat metabolism) with minimal side effects. We propose intranasal oxytocin as a potential novel, effective, and safe therapy for weight loss in human obesity.

Our study was designed to investigate the following:

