2.5. Biostatistical considerations

2.5.1. Sample size and statistical power

Sixty-one participants were randomized to obtain evaluable data for at least 50 participants completing the 8-week treatment period. We conducted power and sample size calculations using 2-sample t-tests at a 2-tailed significance level of $\alpha = 0.05$. The primary endpoint of this study is percent change in body weight from baseline following 8-week intranasal oxytocin treatment compared to placebo; with 25 participants per arm, we have 80% power to detect a between-group (oxytocin versus placebo) mean difference in weight loss of ≥ 3.2 kg, based on a reported

standard deviation for the between-group difference in weight loss of approximately 4 kg in a pilot study of 8-week intranasal oxytocin administration in adults with obesity [35].

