We will conduct regression-based mediation analyses to explore mechanisms underlying the proposed effects of intranasal oxytocin treatment: We will investigate whether (a) the change in brain activation in key reward-related food motivation (VTA, OFC, anterior insula) and homeostatic (hypothalamus) regions during fasted and fed states as well as in cognitive control-related regions (dlPFC, dACC, preSMA) during the fasted state from baseline following 4-week oxytocin treatment mediates change in caloric intake at a test meal 6 weeks from baseline, (b) the change in caloric intake at 6 weeks from baseline mediates the percentage change in body weight at 8 weeks from baseline, and (c) the change in REE at 6 weeks from baseline mediates the percentage change in body weight at 8 weeks from baseline.

Safety and compliance endpoints (assessed at each study time point) will be reported and tested for between-group (oxytocin versus placebo) differences. Endpoints regarding the off-treatment follow-up study time point (week 14 visit) will be reported and analyzed using MMRM in relation to baseline and end of treatment (week 8 visit) time points where appropriate (separately from on-treatment analyses).

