N (%) of in-trial period treatment-emergent adverse events (AE), AE-related discontinuations	Safety endpoint	Categorical/Count	χ^2 test (oxytocin vs. placebo) for severity categories (mild, moderate, severe)
N (%) of total expected study drug doses administered per subject	Treatment adherence	Count	Descriptive statistics: N (%) with compliance $\geq 80\%$

4 – Off-treatment follow-up (W14)

Variable	Use/Objective	Variable type	Statistical model
Body weight, anthropometrics, caloric intake, metabolic profile, psychological, behavioral and quality of life assessments, safety	Follow-up (sustained effects) and safety	Continuous	Descriptive statistics, MMRM (separate analysis)

Figure 3. Proposed statistical analysis plan.

Abbreviations: F, female; M, male; BMI, body mass index; BL, baseline visit; W, week of visit; REE, resting energy expenditure; QTc, QT corrected; EKG, electrocardiogram; IBW, ideal body weight.

For study endpoints, main contrasts are stated (e.g., Δ_{W8-BL}); further contrasts may be investigated as appropriate and according to assessment time points of endpoint variables (Table 2).

Declaration of interests

The authors declare that they have no known competing financial interests or personal relationships that could have appeared to influence the work reported in this paper.

The authors declare the following financial interests/personal relationships which may be considered as potential competing interests:

[name] served on the scientific advisory board and has a financial interest in OXT Therapeutics, Inc.

[name] also received funding for an investigator-initiated study by Tonix Pharmaceuticals.

All other authors declare no conflicts of interest.

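### The Discussion says the trial is powered to determine safety, but the only power figure is for weight and the planned adverse-event comparison is a significance test without a confidence interval

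*Combined protocol and SAP*

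**What the plan says.** The Discussion (section 4) names three purposes under one claim of power: "We have carefully designed and powered this randomized controlled double-blind trial to determine the efficacy, safety, and underlying mechanisms".

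Section 2.5.1 holds the only power calculation: "with 25 participants per arm, we have 80% power to detect a between-group (oxytocin versus placebo) mean difference in weight loss" of at least 3.2 kg, with a standard deviation of about 4 kg, by a two-sample t-test at two-sided 5%. No power, precision, target event rate or margin is given for safety, or for mechanisms.

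On safety, section 2.5.3 says: "Safety and compliance endpoints (assessed at each study time point) will be reported and tested for between-group (oxytocin versus placebo) differences". Figure 3, part 3, lists the number and percentage of treatment-emergent adverse events and of discontinuations due to them, with a chi-square "test (oxytocin vs. placebo) for severity categories (mild, moderate, severe"). It specifies no interval for the difference between arms and does not make clear whether events or participants are counted.

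Section 2.1 expects weight and fat loss "via effects on eating behavior, REE, and fat metabolism) with minimal side effects" and proposes oxytocin as a safe therapy. It sets no threshold for what would count as minimal.

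**The concern.** A claim of power tells the reader that a relevant effect would probably have been found. For weight the plan backs that claim with a calculation. For safety it does not.

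The form of the analysis adds to this. The safety expectation is one of little harm, and a test for a difference cannot confirm little harm; it can only fail to find a difference. With about 30 participants per arm such a failure can occur often even when a sizeable excess is real. Without an interval, the report would not show how large an excess remains compatible with the data. At stake is the strength of the safety statement. The primary weight analysis is not affected.

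**Working it through.** **1. The plan's own figure (weight).** Inputs from section 2.5.1: difference 3.2 kg, SD 4 kg, 25 per arm, two-sided alpha 0.05.

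- Standard error = 4 × √(2/25) = 1.131; 3.2 / 1.131 = 2.83.
- Normal approximation: power = Φ(2.83 − 1.96) = Φ(0.87) = 80.7%.
- Noncentral t: 79.1%.

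The stated 80% is reproduced, and it concerns weight only.

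**2. Inputs for safety.** From the documents: 61 randomized, 1:1. Assumed: a 30/31 split (arm sizes are not given), all 61 analysed, two-sided 5% (no level is stated for the safety tests), and a range of event rates (none is given). The test is the uncorrected Pearson chi-square on a 2×2 table of participants with and without at least one event.

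**3. Hand check for 20% (placebo, n = 30) versus 40% (oxytocin, n = 31).**

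- Pooled rate = (6 + 12.4)/61 = 0.302.
- Null SE = √[0.302 × 0.698 × (1/30 + 1/31)] = 0.1175.
- Alternative SE = √(0.16/30 + 0.24/31) = 0.1143.
- Power = Φ[(0.20 − 1.96 × 0.1175)/0.1143] = Φ(−0.27) = 39.5%.

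**4. Exact power.** All possible tables are enumerated and the binomial probabilities of those with p < 0.05 are summed. A range means that the odd participant was placed in one arm or the other.

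| Placebo → oxytocin | Power | Missed |
|---|---|---|
| *20-point excess* | | |
| 10% → 30% | 52% | 48% |
| 20% → 40% | 41-42% | 58-59% |
| 30% → 50% | 35-37% | 63-65% |
| 40% → 60% | 33% | 67% |
| 50% → 70% | 35-37% | 63-65% |
| *Doubling* | | |
| 5% → 10% | 10-11% | 89-90% |
| 10% → 20% | 20-21% | 79-80% |
| 20% → 40% | 41-42% | 58-59% |
| 30% → 60% | 64-67% | 34-36% |
| 40% → 80% | 91-92% | 8-9% |

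With 25 per arm, 20% versus 40% has 35% power. By the formula in step 3, 80% power for that contrast needs 82 per arm.

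**5. What an interval would show.** Take 12/30 on oxytocin and 6/31 on placebo as an illustration.

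- Chi-square = 3.12, p = 0.08.
- Risk difference = 0.400 − 0.194 = 0.206.
- Wilson limits are 0.246 to 0.577 (oxytocin) and 0.092 to 0.363 (placebo).
- Newcombe lower limit = 0.206 − √[(0.400 − 0.246)² + (0.363 − 0.194)²] = −0.02.
- Newcombe upper limit = 0.206 + √[(0.577 − 0.400)² + (0.194 − 0.092)²] = 0.41.

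The test is non-significant, yet an excess of up to 41 percentage points is compatible with the data.

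**6. No events.** With 0/30 on oxytocin, the exact two-sided 95% upper limit is 1 − 0.025^(1/30) = 11.6%.

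**The case against.** The strongest reply is that the power section claims power only for weight, that one loosely worded Discussion sentence should not carry much, and that a 61-person, 8-week trial without power for adverse events is ordinary. That stands, and it is why the point is minor.

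Three stronger readings are tempting, and the documents do not support them.

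- **That a non-significant test will be taken as proof of safety.** No section states such a rule. Low side-effect burden is a background expectation in section 2.1, and Aims 1 and 2 contain no safety hypothesis. Section 2.6 does cite earlier studies in which "no serious adverse events were reported and there were no differences in adverse events between oxytocin and placebo groups", but it relies on a review of 38 trials as well as the pilot, and the Introduction says that the pilot was small and did not assess safety.
- **That the chi-square test is the only safety tool.** Section 2.3 describes CTCAE grading and review of expectedness and relatedness. Section 2.7 describes an independent monitoring board and expedited reporting. These protect participants and characterize single events, but none of them quantifies the excess risk compatible with the data.
- **That a doubling is missed about 60% of the time.** This needs a placebo rate of 20%, which is not in the documents. If adverse events are common, a doubling would usually be detected.

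The computed test is also simpler than the planned comparison across severity categories, so the figures are indicative of that analysis and not exact for it.

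**Conclusion.** The point holds in a limited form. The plan claims power for safety, and nothing in it shows that the design has that power. The one specified between-arm comparison of adverse events would miss a 20-point excess about half to two-thirds of the time for placebo rates of 10% to 50%. For a doubling, the miss rate runs from about 90% at a 5% base rate to 8-9% at 40%. All of this rests on the assumed 30/31 split, the assumed event rates, and a 2×2 test at two-sided 5% on participants.

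The finding is an unsupported claim and an analysis that leaves its uncertainty unstated. It is not a documented intention to infer safety from a null test. Severity: minor.

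**What to change.** 1. In the Discussion, say that the trial is powered for weight loss only and that safety is estimated. Mechanisms have no power figure either and should not fall under the claim.
2. In section 2.5.3 and Figure 3, part 3, state that participants are the unit, each counted once. Report the oxytocin-minus-placebo risk difference with a 95% confidence interval (Newcombe or exact) for any treatment-emergent adverse event, any moderate-or-worse event, any serious event, and discontinuation due to an adverse event. Where no events occur on oxytocin, give the exact upper 95% limit.
3. Add a sentence that a non-significant between-group test is not evidence of no harm, and keep the chi-square test as descriptive.

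This costs a few sentences and some intervals from data already collected, with no extra participants or visits. The only downside is a slightly less favourable safety statement.
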